FULL TITLE OF THE CLINICAL STUDY

What is the clinical experience of maintaining patient safety in hospital in patients with temporary or permanent loss of cognitive function? A Mixed Methods Study

Protocol Final Version 1.0 06.11.2024
(Last updated 11.05.2026)

Short title: Clinical Experience of Maintaining Patient Safety in Hospital

Acronym: CEMPSIH

IRAS Project ID: 347285

Study Sponsor: University of Nottingham

Sponsor reference: **24065**

Funding Source: This study is part of a PhD study funded by a scholarship awarded by the Engineering and Physical Sciences Research Council (EPSRC).

STUDY PERSONNEL AND CONTACT DETAILS

Sponsor: Contact name	University of Nottingham [name] Head of Research Integrity, Governance & Compliance University of Nottingham [name] [contact]
Chief investigator:	Asst. [name] Associate [name] Human Factors Research Group Faculty of Engineering University of Nottingham Phone: Email: [contact]
Co-investigators:	
[name] [name] Principal Research Fellow, NIHR MindTech Research Centre Institute of Mental Health Email: [contact]
 
[name] Principle Research Fellow Centre for Rehabilitation and Ageing Research School of Medicine, Queens Medical Centre Email: [contact]
 
[name] Student ID: [name] Human Factors Research Group [contact] Email: [contact]

Study Coordinating Centre:	Human Factors Research Group Faculty of Engineering, University of Nottingham, [name]

SYNOPSIS

Title	What is the clinical experience of maintaining patient safety in hospital in patients with temporary or permanent loss of cognitive function? A Mixed Methods Study
Short title	Clinical Experience of Maintaining Patient Safety in Hospital (CEMPSIH)
Chief Investigator	Associate [name]
Objectives	To test whether there is a universal professional experience of maintaining patient safety in hospitals, with patients who have impaired cognitive function
Study Configuration	Mixed Methods, Multi-centre, Exploratory Sequential Strategy
Setting	Secondary care - Acute Hospital Trusts
Number of participants	128 participants overall. Up to 32 participants per Hospital (16 Nursing staff, 8 Therapists and 8 Medical Doctor or associates)
Eligibility criteria	Direct patient facing healthcare workforce responsible for managing and preventing accidental falls in the NHS.

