Description of interventions	Observations of participants during a simulation of an in-patient safety scenario, followed by a semi structured focus group discussion. TThe simulation will be repeated 8 times over 2 days in each participating institution. This will require up to 128 participants delivering 16 datasets.
Duration of study	The study will start on November 28 th 2024 or when necessary approvals have been received. The study will be completed within 6 months of start date. Each participant will be required for a total of 4 hours in 1x 3.5 hour session and a further feedback session of 30 minutes on completion of study.
Methods of analysis	Observations will inform focus group discussion and themes and codes derived from focus group discussion will be analysed using Nvivo 14.

ABBREVIATIONS

CI	Chief Investigator overall
CDM	Critical Decision Method
CEIFP	Clinical Experience of In-patient Fall Prevention (Short study title)
CG	Clinical Guidance
CRF	Case Report Form
DMP	Data Management Plan
EPSRC	Engineering and Physical Sciences Research Council
GCP	Good Clinical Practice
MFA	Multifactorial Assessment
NHS	National Health Service
NICE	National Institute for Health and Care Excellence
PI	Principal Investigator at a local centre
PIS	Participant Information Sheet
RCT	Randomised Controlled Trial
REC	Research Ethics Committee
PPI	Patient and Public Involvement
R&D	Research and Development department
TRL	Trial Recruitment Log (participants demographics)
UoN	University of Nottingham

TABLE OF CONTENTS

STUDY PERSONNEL AND CONTACT DETAILS	2
ABBREVIATIONS.....	4
STUDY BACKGROUND INFORMATION AND RATIONALE.....	7
STUDY OBJECTIVES AND PURPOSE	8
PURPOSE	8
PRIMARY OBJECTIVE	8
SECONDARY OBJECTIVES	8
STUDY DESIGN	9
STUDY CONFIGURATION	9
STUDY MANAGEMENT	10
DURATION OF THE STUDY AND PARTICIPANT INVOLVEMENT	11
End of the Study	11
SELECTION AND WITHDRAWAL OF PARTICIPANTS	12
Recruitment	12
Eligibility criteria	12
Inclusion criteria	12
Exclusion criteria	13
Expected duration of participant participation	13
Participant Withdrawal	13
Informed consent	13
STUDY REGIMEN	14
Compliance	15
Criteria for terminating the study	15
ANALYSES.....	17
Methods	17
Sample size and justification	17
ADVERSE EVENTS	18
ETHICAL AND REGULATORY ASPECTS	18
ETHICS COMMITTEE AND REGULATORY APPROVALS	18
INFORMED CONSENT AND PARTICIPANT INFORMATION	18
RECORDS	19
Case Report Forms	19
Source documents	19
Direct access to source data / documents	19
DATA PROTECTION	20
QUALITY ASSURANCE & AUDIT	20

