- To disprove the null hypothesis that “there is no universal clinical experience of accidental fall prevention in hospitals with patients who have impaired cognitive function”.

SECONDARY OBJECTIVES

[figure not shown]
- To inductively generate a questionnaire to be distributed to healthcare professionals and care workers in a future study.
- To gather an evidence base for the co-created design and testing of fall prevention interventions as part of the longer term PhD project

The investigator has completed the HRA tools which have confirmed the study is classed as research and that it does not require NHS REC review. The investigator has also successfully undertaken the Good Clinical Practice training to provide public assurance that the rights, safety and wellbeing of research participants are protected and that research data are reliable.

STUDY DESIGN

STUDY CONFIGURATION

This is a multi-centre qualitative study utilising a purposive sampling strategy. Healthcare workers directly involved in preventing falls in hospital will be invited to contribute to the study via an email from their ward manager or clinical lead. Participants will be asked to respond directly to the researcher to indicate their interest in the study. They will be selected to ensure Medical and Surgical wards are represented to ensure generalisability of outcomes. Overall aim will be for up to 16 participants from the nursing team, registered and unregistered, up to 8 therapist participants and up to 8 doctors (*Figure 1- Participant Study Flowchart*).

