The focus group will be recorded, transcribed and analysed using Nvivo 14 (a software application to assist with coding) assigning meanings through essence capturing (Saldaña, 2021) by creating codes. These codes will be generated for the purpose of pattern detection to interpret data and deduct meaning (Vogt et al., 2012). This can be interpreted as imposing values or as reductionist but using constructivist principles will allow valuing multiple perspectives and will establish a deeper understanding of staff experience (Creswell, 2018). It is difficult to completely remove the investigator's values when analysis is done, but by sharing the analysis with the participants and the research team there is transparency and reflexivity, recognising the 'importance of self' (Humphries, 2003). The analyses will be discussed with the participants so any disagreement will also be recorded for the reader to consider. The primary intent of the qualitative phase is to design a measure that is grounded in issues raised by patient facing staff and PPI representatives rather than individual opinion or experience.

Sample size and justification

The investigator is seeking to involve a small number of relevant direct patient facing healthcare workers to provide in depth information about the lived experience of preventing and managing in-patient falls. By purposefully involving participants who are charged with preventing in-patient falls as part of their usual practice the investigator will be able to collect in depth knowledge of the experience and associated heuristics. 8 simulations and focus groups in 4 different hospitals on different geographical sites are planned generating 16 datasets. The investigator will continue until repeated themes suggests there is a degree of homogeneity in experiences or not (Creswell, 2018). This is with the intention of adopting a phenomenological approach but depending on the data arising sampling could continue to allow grounded theory to inform the questionnaire (Creswell, 2023). The final sample size will

not be determined until a sufficient database has been collected to develop the content of the questionnaire for a future study.

ADVERSE EVENTS

The occurrence of an adverse event as a result of participation within this study is not expected and no adverse event data will be collected.

ETHICAL AND REGULATORY ASPECTS

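### The rule for ending sampling is the same judgement as the primary conclusion, has no operational threshold, and allows a stop before all planned Trusts are sampled

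*Combined protocol and SAP*

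**What the plan says.** The primary objective is to disprove the null hypothesis that "there is no universal clinical experience of accidental fall prevention in hospitals with patients who have impaired cognitive function". The Synopsis puts it as "To test whether there is a universal professional experience of maintaining patient safety in hospitals".

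Sample size and justification makes four statements about size:

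- The plan: "8 simulations and focus groups in 4 different hospitals on different geographical sites are planned generating 16 datasets".
- The rule for ending: "The investigator will continue until repeated themes suggests there is a degree of homogeneity in experiences or not".
- A possible extension: "depending on the data arising sampling could continue to allow grounded theory to inform the questionnaire".
- The total, left open: it is to "not be determined until a sufficient database has been collected to develop the content of the questionnaire for a future study".

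The Synopsis gives "128 participants overall" with a per-hospital maximum, and later "This will require up to 128 participants delivering 16 datasets". Study configuration and Study duration also word the numbers of hospitals, simulations, focus groups and datasets as upper limits. No section gives a minimum number of groups or Trusts, a definition of homogeneity or of its absence, or a statement of which criterion governs.

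**The concern.** A rule for ending data collection should rest on something other than the answer to the research question. Whether further groups still add new codes would be such a basis. Here the trigger is that experiences look alike, and the primary conclusion is that experience is universal. Once the trigger is met, the conclusion has in effect been drawn.

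Two features add to this. Read literally, a condition of homogeneity *or not* is met by any data at any time, so it constrains nothing. And because the numbers are ceilings, nothing prevents a stop after one, two or three Trusts. What is at stake is how the main finding can be read: a report of agreement across hospitals and professions would carry little weight if hospitals that might have disagreed were left out because the earlier ones agreed.

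**Working it through.** **1. The plan's own figures.** Inputs are 4 hospitals, 8 simulations per hospital, 4 participants per simulation (2 nursing, 1 therapist, 1 doctor) and 2 simulations per focus group, from Study configuration, its participant table, Methods and Compliance.

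- Simulations: 4 × 8 = 32
- Participants: 32 × 4 = 128
- Focus groups (datasets): 32 / 2 = 16, or 4 per hospital

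All three agree with the document. They follow from the session timetable and not from a saturation or precision criterion.

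**2. The two criteria side by side.** The primary objective asks whether experience is universal. The stopping rule asks whether experience is homogeneous. These are the same judgement, and the document defines neither separately.

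**3. What an early stop could miss.** The document gives no frequency for divergent experience, so a range is assumed. If a share d of focus groups would voice a divergent experience, and groups are independent, the chance that none of n groups voices it is (1 − d)^n.

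| d (assumed) | n = 4 (one Trust) | n = 16 (all planned) |
|---|---|---|
| 10% | 0.9^4 = 66% | 0.9^16 = 19% |
| 20% | 0.8^4 = 41% | 0.8^16 = 3% |
| 30% | 0.7^4 = 24% | 0.7^16 = 0.3% |

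Groups come four to a Trust. If groups within a Trust resemble one another, the chance of missing divergence at a given n is higher than shown. The table describes small samples in general. It shows what completing the plan buys, and it does not measure this particular rule.

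**4. Does the rule lean one way?** Let q be the assumed chance that a group repeats a theme. Call the experience homogeneous if at least 75% of groups repeat it and not homogeneous if at most 25% do. Compare one look at 16 groups (at least 12 of 16) with a look after every group from the 4th, computed exactly by removing at each look the paths that have met a threshold. None of these settings is in the document.

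| q | One look: homogeneous | Repeated looks, stop only for homogeneity | Repeated looks, two-way stop: homogeneous | Two-way stop: not homogeneous |
|---|---|---|---|---|
| 0.4 | 0.5% | 19.0% | 19.0% | 54.3% |
| 0.5 | 3.8% | 34.5% | 34.4% | 34.4% |
| 0.6 | 16.7% | 54.7% | 54.3% | 19.0% |

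Letting the emerging answer decide when to stop makes a call of homogeneity far more frequent. With a two-way stop at q = 0.5, the opposite call is made equally often. Tying the stop to the answer therefore matters, but it does not by itself favour one conclusion.

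**The case against.** A reader might infer that the rule is built to produce a universal experience. The text does not support that. It also allows a stop on non-homogeneity, and a rule that any data can satisfy is empty, which is different from directional. Part 4 of the working agrees. A lean would follow only if repetition were the sole working trigger. Repetition is the only evidence the sentence names, but the document does not settle that reading.

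A reader might also infer that the sizes contradict each other. They mostly do not: a planned maximum is compatible with a final number still to be decided. The one open question is whether the continuation wording permits going above 128.

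Nor does the document show the judgement being made during the two days at a Trust, before coding. Study regimen places transcription and analysis after the session, and Study duration ties completion to groups having been analysed and themed together.

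The strongest defence is that homogeneity is not the only gate. The continuation and questionnaire-sufficiency statements can lengthen sampling, and the second serves the stated aim of designing a measure. Methods also shares the analysis with participants and the research team and records disagreement. This has weight for interpretation. But none of these provisions sets a minimum, is given a role in the decision to stop, or is said to override the homogeneity rule. No early stop is scheduled, but none is prevented.

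**Conclusion.** The point holds in this form: the stopping criterion coincides with the primary conclusion, is not operational, and, with only ceilings on size, allows sampling to end on apparent agreement before all Trusts are seen. Parts 1 and 2 of the working rest on the document alone.

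The size of the effect cannot be computed from the document. On the assumed 10% to 30% range with independent groups, stopping after one Trust leaves a 24% to 66% chance of having seen no divergent group, against 0.3% to 19% after all 16. A bias toward universality is a risk to guard against and has not been demonstrated.

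**What to change.** Replace the stopping sentence in Sample size and justification with:

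> Data collection will cover all planned Trusts (16 focus groups, within the stated 128 participants) whether or not experiences appear homogeneous; agreement between groups is not a reason to stop. The number of new codes contributed by each successive focus group and Trust will be reported as evidence of adequacy.

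Do not add an allowance to stop after fewer Trusts, since that would restore the problem. Keep the grounded-theory and questionnaire-sufficiency text only as a possible reason to continue after the planned groups. State that it does not permit an earlier stop, and whether continuing may exceed 128. If groups are lost for rostering or recruitment reasons, report that as the reason, so that it is not read as saturation.

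The cost is a wording change and a running count of new codes, with no enrolment beyond the planned maximum. The downside is losing the option to stop early on impression.
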